### **Study Stopping and Pausing Rules**

The study will pause enrollment and stop treatment for all participants if any of the following events occur pending submission to Regulatory Agencies and review by the DSMC and IRB who will determine if the study may resume:

- Any event of treatment related death in a study subject

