## 6.2 Ascorbate Therapy

- 6.2.1 **Dose reductions** – As per Table 1 (below) if there is a DLT (Section 5.6)

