**Table 1. Phase 1b Dose De-escalation Schedule**

Number of Patients with DLT at a Given Ascorbate Dose	Decision Rule
$\geq 2$	Dose level will be declared toxic. If this is the lowest dose level, stop the study due to excessive toxicity; otherwise enter three additional patients at the next lowest dose level.
$\leq 1$ out of 3	Enter three more patients at this dose level.
$\leq 1$ out of 6	This is the recommended dose for the subsequent Phase2.

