## 6.3 Dose Limiting Toxicities

### Definitions of dose-limiting toxicity:

Toxicity will be evaluated according to CTCAE version 5.0. DLT will be defined as any of the following ascorbate related toxicity or related to the combination of pharmacologic ascorbate and radiation therapy during treatment and up to 28 days after the first pharmacologic ascorbate infusion:

- Infection grade 4
- SAE per 21CFR312.21 with an attribution of *possible, probable, or definite* to ascorbate
- Grade 3 diarrhea or nausea/vomiting despite maximal support
- Any grade 3/4 or greater hematologic or non-hematologic toxicity not explainable by another cause in the opinion of the principal investigator, with the exceptions of:
  - Expected radiation related skin toxicity of any grade.
  - Brief (< 1 week) grade 3 fatigue.

If unexpected DLT occurs, ascorbate administration should be delayed until the DLT has resolved to at least CTCAE version 5.0 grade 1 or baseline and future dose be reduced to dose level -1 as per table 1. If dosing is delayed by more than 4 weeks due to the occurrence of unexpected adverse event or if a patient already dose reduced to level -1 (62.5 gm/dose) experiences another DLT that is considered related to ascorbate, then the subject should be taken off study.

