## 12. STATISTICAL CONSIDERATIONS

### 12.1 Phase Ib

The primary objective of the Phase Ib portion of this study is to confirm the current standard dose of intravenous ascorbate, 75 gm, utilized in patients diagnosed with pancreatic cancer also receiving concurrent chemo radiation is safe within this population of sarcoma patients being treated concurrently with pre-operative radiation. Up to six (6) patients will be recruited to the standard dose, 75 grams administered intravenously 3 times a week during radiation therapy (5 weeks). If at most 1 out of 6 patients experience a DLT, the standard dose will be considered safe. If 2 or more patients experience a DLT, the next cohort of patients will be assigned to dose level - 1. The recommended phase II dose (RP2D) will be defined as the highest dose level for which at most 1 out of 6 patients experience a DLT.

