### 12.3 Sample Size/Accrual Rate

The Phase I portion of this study is expected to require 6 evaluable patients (min 6, max 12). Patients treated in Phase Ib at the RP2D will also be included in the Phase II portion. Additional evaluable patients will be accrued for a total of 25 patients treated at the RP2D. The anticipated accrual rate is 2 patients per month who would meet inclusion criteria.

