### Additional Reporting Requirements:

- A scanned copy of the completed eligibility checklist, with screening information and PI signature, will be attached in OnCore for ongoing review by DSMC staff.
- Serious adverse events will be entered directly into an OnCore SAE report by the research team. OnCore will send an automatic notification to the DSMC Chair/acting Chair and staff for review.
- The DSMC utilizes a risk-based monitoring approach. The trial's research records will be monitored at minimum twice per year. Monitoring may be done more frequently depending on the protocol, risks to subjects, reported serious/adverse events, patient population and accrual rate. Records for a minimum of 25% of subjects will be monitored for the entire study.

Monitoring will involve the following:

- review eligibility of patients accrued to the study,
- check for the presence of a signed informed consent,
- determine compliance with protocol's study plan,
- determine whether SAEs are being appropriately reported to internal and external regulatory agencies,
- compare accuracy of data in the research record with the primary source documents,
- review investigational drug processing and documentation,
- assess cumulative AE/SAE reports for trends and compare to study stopping rules.

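### Once six patients have cleared the dose, the plan fixes no number of non-fatal DLTs at which Phase 2 enrolment pauses; a fixed trigger and one DLT window would be a cheap, modest improvement

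*Combined protocol and SAP*

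**What the plan says.** Section 12.1 sets the clearing rule for Phase 1b: "If at most 1 out of 6 patients experience a DLT, the standard dose will be considered safe". Two or more DLTs send the next cohort to 62.5 g. Table 1 in Sections 5.2 and 6.2 carries the same rule under a Phase 1b title. Section 12.3 carries the Phase 1b patients treated at the RP2D into Phase 2: "Additional evaluable patients will be accrued for a total of 25 patients treated at the RP2D". Section 12.2 gives a Phase 2 decision rule for pathologic response only.

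Appendix D, under Study Stopping and Pausing Rules, has one bullet: "Any event of treatment related death in a study subject". Its lead-in pauses enrolment and also stops treatment for everyone on study. Under Additional Reporting Requirements, monitors are told to "assess cumulative AE/SAE reports for trends and compare to study stopping rules".

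Section 6.3 counts DLTs "during treatment and up to 28 days after the first pharmacologic ascorbate infusion" and excludes "Expected radiation related skin toxicity of any grade". After a DLT, that patient's ascorbate is held and then reduced. Section 5.2 has the first Phase 1b patients monitored until surgery, when safety is assessed.

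**The concern.** Monitors are asked to compare cumulative events with stopping rules, but for Phase 2 those rules contain nothing non-fatal to compare with. Six patients say little about the DLT rate, so a dose with an undesirable rate can clear and then be given to 19 more people. How many DLTs should halt enrolment would be decided only as they accumulate.

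The counting window is a related problem. A toxicity that appears after the last infusion but before surgery is outside Section 6.3 for a patient who finished treatment, yet inside the Phase 1b monitoring period of Section 5.2. Two readers could classify it differently, and that affects the 1-in-6 clearance count as well as any Phase 2 count.

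**Working it through.** **The plan's own figure.** With n = 25 and success at 6 or more responses, the exact binomial gives a one-sided level of 0.033 at a 10% response rate and power of 0.807 at 30%. This matches the stated 0.03 and 81%. The efficacy design is sound and is not affected here.

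**Inputs.** Clearing rule of at most 1 DLT in 6 (Section 12.1). Total of 25 at the RP2D and accrual of 2 patients per month (Section 12.3). Five weeks of treatment (Section 12.1). Surgery 4 to 6 weeks after radiation (Section 5.1). Reviews at least twice a year (Appendix D, Study Safety Review). The plan names no unacceptable DLT rate, so the true rate p is an assumption shown over a range.

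**Exposure after clearance.** 25 − 6 = 19 patients, if exactly six were treated at the RP2D in Phase 1b. At the minimum review interval, 2 × 6 = 12 of them could enrol between two reviews.

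**What six patients show.** Exact 95% confidence intervals for the DLT rate are 0% to 46% after 0 of 6, and 0.4% to 64% after 1 of 6.

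**Chance of clearing.** P(clear) = (1 − p)^6 + 6p(1 − p)^5. At p = 1/3 this is 0.088 + 0.263 = 0.351.

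**Illustrative boundary.** Pause at 4 or more DLTs in the first 12 patients, or 6 or more in the first 18, with the Phase 1b patients included. The calculation conditions on 0 or 1 DLT in the first six and enumerates the later patients. At p = 1/3, cleared trials have 0 DLTs with probability 0.25 and 1 with probability 0.75. The chance of reaching 4 by patient 12 is 0.25 × 0.100 + 0.75 × 0.320 = 0.265. A further 0.127 reach 6 by patient 18, for a total of 0.392.

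| True DLT rate | P(clear) | P(pause given clear), 4/12 or 6/18 | P(clear and pause) | P(pause given clear), 5/12 or 7/18 |
|---|---|---|---|---|
| 10% | 0.886 | 0.008 | 0.007 | 0.001 |
| 17% | 0.729 | 0.053 | 0.038 | 0.009 |
| 20% | 0.655 | 0.090 | 0.059 | 0.020 |
| 25% | 0.534 | 0.180 | 0.096 | 0.054 |
| 33% | 0.351 | 0.392 | 0.138 | 0.174 |
| 40% | 0.233 | 0.580 | 0.135 | 0.328 |
| 50% | 0.109 | 0.815 | 0.089 | 0.605 |

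**DLTs spared, if nobody would otherwise act and every pause is permanent (4/12 or 6/18).**
- Accrual ends at patient 12 or 18. At p = 1/3: (13 × 0.265 + 7 × 0.127)/3 = 1.44 given clearance, and 1.44 × 0.351 = 0.51 per trial started. At 40% and 50% the per-trial figures are 0.60 and 0.51.
- Accrual ends the moment the count is reached. Given clearance, 1.6, 2.9 and 5.2 at 33%, 40% and 50%. Multiplied by P(clear), about 0.6, 0.7 and 0.6 per trial started.
- With patients still in their counting window when the pause comes (35 days of treatment plus 30 days: 2 × 65/30.44 = 4.3 patients). Per trial started, 0.31, 0.37 and 0.32.
- At a true 10%, 0.01 given clearance.

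These figures count clearance at 75 g only, and the boundary only up to patient 18.

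**Wound complications.** Section 5.7.11 expects them in about a third of patients. If they counted, the same boundary would be crossed with probability 0.607 + 0.081 = 0.688, without conditioning on clearance. They should stay outside it.

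**Window.** Day 28 after the first infusion falls within a five-week course. For a patient who completes treatment, the Section 6.3 window therefore ends with treatment, and the 28-day clause extends it only for those who stop early. Surgery falls at about weeks 5 + 4 = 9 to 5 + 6 = 11.

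**The case against.** The strongest reply is that nobody would ignore four DLTs in twelve patients. At this single institution, the principal investigator attributes every grade 3 or higher event (Section 7.1). Routine adverse events are open to the sponsor, a medical monitor and the DSMC (Section 7.4). SAEs reach the DSMC within a business day or 24 hours (Section 7.5; Appendix D). Subject summaries are continually available to the DSMC, and monitoring can be intensified when events or accrual call for it. Section 1.3 also reports no DLTs in nine pancreatic patients and no grade 3 toxicity in the glioblastoma and lung study.

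Most of this stands. The trial does not lack safety oversight, and a reader who infers that it does would be wrong. The 12 patients between reviews are a worst case at the minimum schedule, and the DLTs spared are measured against an unrealistic assumption of inaction. What remains is that all these routes are discretionary. DLTs that are not SAEs have no expedited route, and none of these routes fixes a count. The earlier studies were in other diseases, and Section 5.2 says the combination has not been studied in sarcoma.

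A reader might also infer that Table 1 already limits Phase 2, because Section 6.2.1 cites it without naming a phase and the row for two or more DLTs has no denominator: "Dose level will be declared toxic. If this is the lowest dose level, stop the study due to excessive toxicity". The table's title, its rows for 3 and 6 patients and its reference to the Phase 2 that follows confine it to Phase 1b. The documents do not support a limit of two DLTs in 25. That row does show that a non-fatal stopping rule exists in Phase 1b, so the gap is in Phase 2 only.

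Finally, the choice of boundary is a matter of judgement. That is fair: the one above is an example for the sponsor and DSMC to accept or replace.

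**Conclusion.** The point holds as a cheap safety improvement of modest size. It does not correct an error. For the 19 patients after clearance, the only pre-specified study-level pause trigger is a treatment-related death. A simple boundary would pause 39% to 81% of cleared trials at true DLT rates of 33% to 50%. Its price is an unnecessary pause in about 1% to 9% of cleared trials at 10% to 20%, and 18% at 25%. The benefit is about 0.5 to 0.6 DLTs per trial started at 33% to 50%, slightly more if the pause takes effect at once and 0.3 to 0.4 with patients already in the pipeline. It is close to none at 10%. All of this assumes the stated true rates, permanent pauses and no discretionary action, so the real gain is smaller.

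The window inconsistency between Sections 6.3 and 5.2 is real but narrow. It would go too far to call the 28-day clause empty, because it keeps patients who stop treatment early under observation.

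**What to change.** 1. Add a separate sentence to Appendix D that pauses enrolment only, for DSMC review. The trigger is a Section 6.3 DLT in 4 or more of the first 12, or 6 or more of the first 18, patients started at the RP2D, acting as soon as the count is reached. Include the Phase 1b patients, count one DLT per patient, and keep patients later reduced in dose. State how the boundary continues for patients 19 to 25, which the figures above do not cover. The sponsor and DSMC may prefer 5/12 and 7/18, which give fewer unnecessary pauses but detect less. Section 12.2 should state the operating characteristics of the rule chosen. It should not be a second bullet under the existing rule, because that lead-in would also stop treatment for patients in mid-course. Enrolment need not wait for a look.

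2. Use one DLT window in both phases: from the first infusion at the assigned dose to 30 days after the last, or to surgery if earlier. This fits the adverse-event recording period already in Appendix D. State that post-operative wound complications and expected radiation skin toxicity are outside the count. Wound complications and Grade 3-4 dermatitis stay under the historical-control comparison in Section 12.2.

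The cost is a few lines in an amendment and one running count from data already in OnCore, with no new committee, visits or data collection. The downside is the unnecessary-pause risk given above.

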### **FDA Reporting Requirements (for Sponsor-Investigators)**

It is the responsibility of the IND sponsor-investigator to comply with IND safety reporting as set forth in the Code of Federal Regulations, [Section 312.32](#). This responsibility includes providing an annual IND report to the FDA.

All IND safety reports must be submitted on [Form 3500A](#) and be accompanied by [Form 1571](#). The type of report (initial or follow-up) should be checked in the respective boxes on Forms 3500A and 1571. See [Instructions for completing Form 3500A](#). Please note all instance of UIHC, location, and faculty / staff should be redacted from supporting documentation and the 3500A.

The submission must be identified as:

- “IND safety report” for 15-day reports, or
- “7-day IND safety report” for unexpected fatal or life-threatening suspected adverse reaction reports, or
- “Follow-up IND safety report” for follow-up information.

For detailed explanation of the above definitions, requirements, and procedures related to IND application safety reports and the responsibilities of IND applications sponsors with regard to such reporting, refer to [Guidance for Industry and Investigators: Safety Reporting Requirements for INDs and BA/BE Studies \(PDF - 227KB\)](#)

In addition to completing appropriate patient demographic and suspect medication information, the report should include the following information within the Event Description (section 5) of the MedWatch 3500A form:

- Treatment regimen (dosing frequency, combination therapy)

- Protocol description (and number, if assigned)
- Description of event, severity, treatment, and outcome, if known (grading the event per CTCAE)
- Supportive laboratory results and diagnostics
- Sponsor-Investigator's assessment of the relationship of the adverse event to each investigational product and suspect medication

## **Data Monitoring and Management**

### Subject Registration

All studies that undergo PRMC review and/or utilize HCCC Clinical Research Services (CRS) resources are required to register subjects in OnCore. Each subject registration includes the following:

- The subject's IRB approved (version date) consent form and the date of their consent.
- Date of eligibility and eligibility status (eligible, not eligible)
- On study date and subject's disease site (and histology if applicable)
- On treatment date (if applicable)

All subject registration information is expected to be entered into OnCore within **2 (two) business days** after the subject's study visit.

### Subject Data

For HCCC investigator initiated trials, research staff are responsible for entering subject study data (data collection) into OnCore electronic case report forms (eCRFs). These eCRFs must be approved by the PI and statistician prior to study activation to ensure sufficient and necessary data acquisition. All information entered into eCRFs will be traceable to the source documents which are generally maintained in the subject's file.

eCRF data entry needs to be timely and should be entered into OnCore as soon as possible but no later than **14 (fourteen) business days** after the subject's visit, including adverse events, tumor measurements, administration of study medication, concomitant medications, labs, and vitals. Physical exam assessments must be entered no later than **14 (fourteen) business days** following completion of the physician's clinic note in the medical record.

Timely data entry facilitates remote monitoring of data, allows the data to progress appropriately through the data cleaning process, and helps prevent a backlog of data queries.

### Forms Monitoring

OnCore eCRF data are monitored on a routine basis (dependent on accrual) to ensure all data are entered completely, accurately, and within time requirements outlined above. The assigned DSMC monitor will coordinate and complete the data monitoring review. When the time comes to monitor a study (based on patient accrual and assigned risk level of trial) the monitor arranges for a selection of cases to be reviewed from among the subjects registered in OnCore. As part of the forms monitoring process, the assigned monitor will issue queries via OnCore (linked to the eCRF) to resolve missing, incomplete, and/or incorrect information. A member of the research team is expected to respond to these monitoring queries within **14 (fourteen) business days**.

The monitoring process can often identify misunderstandings or deficiencies in the written, research protocol requirements earlier in the study process and thereby improve data quality and

reduce rework.

#### Final Reports

A summary of each subject's data record is continually available to the PI, research staff, and DSMC from OnCore's Biostat Console. The availability of this information is a valuable tool for the preparation of final reports and manuscripts as well as ongoing deficiency reports.
